7.7 LOST TO FOLLOW-UP

A subject will be considered lost to follow-up if he/she does not appear for the scheduled study visit for 2 consecutive visits, and study personnel are unable to contact the subject.

Some actively enrolled subjects will not return for follow-up exams on time. Study personnel must make a reasonable effort to contact the subject and document the following contact attempts before declaring a subject to be lost to follow-up: the subject has been contacted according to the site's policies, but no fewer than two documented phone contacts (at least one of these attempted phone contacts conducted by the Investigator) and one written attempt without response. The written attempt can either be a certified letter or an email with read confirmation dependent on accepted ways of communication within the study regions. Copies of all attempts to reach the subjects by mail or email and/or the attempts to contact the subject via other means should be documented, and that documentation should be kept with the subject’s source documents.

CONFIDENTIAL AND PROPRIETARY

This document contains information that is confidential and proprietary to Smith & Nephew PLC and Smith & Nephew, Inc. and is intended for use only by Smith & Nephew and its manufacturer. It shall not be reproduced or copied in whole or in part, nor shall the contents be disclosed by any means without prior written permission from Smith & Nephew, nor shall anyone make any use of it that is contrary to the expressed or implied wishes of Smith & Nephew.

Clinical Protocol	Study Number: OR3O.2019.10 (China)
Prospective, Multi-center, Randomized, Controlled Study to Evaluate the Safety and Efficacy of the OR3O™ Dual Mobility System versus conventional single bearing design Total Hip System in Primary Total Hip Arthroplasty (THA) Procedures	Version: 1.0, 18Aug2020
	Page: 34 of 90

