1. Query subject regarding any changes in general health and the use of concomitant medications. If any adverse events or device deficiencies are observed or reported, they must be recorded as instructed in Section 12 - Adverse Events and Device Deficiencies.
2. Verify with subject if any revision has occurred since last visit. If any revision is observed or reported, it must be recorded as instructed in Section 12 - Adverse Events and Device Deficiencies. Revised components are to be recorded.
3. Complete the HHS.
4. Have the subject complete the EQ-5D-5L questionnaire.
5. Have the subject complete the HOOS JR. questionnaire.
6. Collect radiographic images of the affected hip in AP and lateral view in supine position if not performed at discharge. Investigator to review the images and record data in the subject's medical record.
7. Instruct the subject on returning to the site for the next follow-up visit.
8. In case the follow-up visit was missed, contact the subject by telephone to collect information on implant status and adverse events. Collect the information on the appropriate source document.
9. Transcribe data to the eCRF.

9.1.5 Follow-Up visits at 3 months (90 ±30 days), 6 months (180 ±30 days) and 1 year (365 ±60 days) post-surgery

1. Query subject regarding any changes in general health and the use of concomitant medications. If any adverse events or device deficiencies are observed or reported, they must be recorded as instructed in Section 12 - Adverse Events and Device Deficiencies.
2. Verify with subject if any revision has occurred since last visit. If any revision is observed or reported, it must be recorded as instructed in Section 12 - Adverse Events and Device Deficiencies. Revised components are to be recorded.
3. Complete the HHS.
4. Have the subject complete the EQ-5D-5L questionnaire.
5. Have the subject complete the HOOS JR. questionnaire.

CONFIDENTIAL AND PROPRIETARY

This document contains information that is confidential and proprietary to Smith & Nephew PLC and Smith & Nephew, Inc. and is intended for use only by Smith & Nephew and its manufacturer. It shall not be reproduced or copied in whole or in part, nor shall the contents be disclosed by any means without prior written permission from Smith & Nephew, nor shall anyone make any use of it that is contrary to the expressed or implied wishes of Smith & Nephew.

Clinical Protocol	Study Number: OR3O.2019.10 (China)

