9.2 STUDY METHODS AND MEASUREMENTS

9.2.1 Survivorship

Survivorship of THA is defined as no revision of any of the components of the OR3O™ Dual Mobility System (insert, liner) or controlled product, acetabular shell, femoral head and femoral stem. Information on implant / component survivorship will be derived from adverse event in eCRFs.

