10.4.2 Analysis of Secondary Endpoints

Implant Survivorship

- Survivorship of the OR3O Dual Mobility System (assessed by revision for any reason) will be summarized using Kaplan-Meier survival tables and graphs. Time to revision will be the endpoint of interest, for subjects who die, are lost to follow-up or do not encounter the event of interest by the time of study termination would be censored on these dates.

CONFIDENTIAL AND PROPRIETARY

This document contains information that is confidential and proprietary to Smith & Nephew PLC and Smith & Nephew, Inc. and is intended for use only by Smith & Nephew and its manufacturer. It shall not be reproduced or copied in whole or in part, nor shall the contents be disclosed by any means without prior written permission from Smith & Nephew, nor shall anyone make any use of it that is contrary to the expressed or implied wishes of Smith & Nephew.

Clinical Protocol	Study Number: OR30.2019.10 (China)
Prospective, Multi-center, Randomized, Controlled Study to Evaluate the Safety and Efficacy of the OR30™ Dual Mobility System versus conventional single bearing design Total Hip System in Primary Total Hip Arthroplasty (THA) Procedures	Version: 1.0, 18Aug2020
	Page: 55 of 90

- Survivorship of the controlled system up to 2 years after surgery (assessed by revision for any reason). Kaplan-Meier survival tables analogous to that specified for the OR30 Dual Mobility system will be implemented here as well.

Harris Hip Score (HHS)

- HHS scores for each subject will further be categorized as follows: Excellent (90-100); Good (80-89); Fair (70-79); Poor (60-69) and; Very poor (<60). Shift tables from the preoperative visit to all postoperative visits using these classifications will be generated.

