7.4 Derived Data

Change from pre to postoperative visits

This will be calculated as:

Post – operative value_{*visit* n} – Pre – operative value_(*Visit* 1) where n > 1.

CONFIDENTIAL AND PROPRIETARY

This document contains information that is confidential and proprietary to Smith & Nephew PLC and Smith & Nephew, Inc. and is intended for use only by Smith+Nephew and its manufacturer. It shall not be reproduced or copied in whole or in part, nor shall the contents be disclosed by any means without prior written permission from Smith+Nephew, nor shall anyone make any use of it that is contrary to the expressed or implied wishes of Smith+Nephew.

Statistical Analysis Plan

A Prospective, Multi-center, Randomized, Controlled Study to Evaluate theVersion: 2.0,Safety and Efficacy of the OR3O™ Dual Mobility System versus conventional29-Feb-2024single bearing design Total Hip System in Primary Total Hip Arthroplasty (THA)Page: 15 of 27ProceduresProcedures

Number: OR3O.2019.10 ST: 1100 Version: 2.0, 29-Feb-2024 Page: 15 of 27

Body Mass Index (BMI)

- BMI = {(Weight in kg)/(Height in m)²}, if units are in kg for weight and m for height
- BMI = {(Weight in lbs.)x703.07))/(Height in inches)²}, if units are in lbs. for weight and inches for height (Adjustments made to formula to standardize BMI unit to kg/m²)

Time to Revision

• Time to revision (in months) = (Revision Date – Operative Date + 1)/30.4375.

Hip disability and Osteoarthritis Outcome Score for Joint Replacement (HOOS JR)

The HOOS JR is a short-form survey based on the HOOS that specifically focuses on the outcome after THA. HOOS JR consists of the following 2 items:

- Pain (2 items) and
- Activities of daily living (4 items).

Each item (question) that is used for scoring the HOOS JR is rated on a scale of 0 to 4 as follows:

- \circ 0 = None; 1 = Mild; 2 = Moderate; 3 = Severe and; 4 = Extreme.
- The range of potential sum of raw scores for all 6 items of the HOOS JR is between 0 and 24 where 0 is the best score and 24 is the worst possible score. The maximum allowable number of missing items on the HOOS JR is 2. If more than 2 of the 6 items are missing, the raw HOOS JR score will not be computed. If 1 or 2 of the item scores are missing, the rounded average of the other non-missing items for that subject will be imputed. An interval score from 0-100 (0 indicating total hip disability and 100 indicating perfect hip health) is extrapolated from the sum of the HOOS JR item scores [1].

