7.11 Analysis of Secondary Endpoints

All secondary endpoints will be summarized using the SAF analysis population. Changes from preoperative to postoperative will not be analysed for PROMs due to early termination of the study. Summary statistics for observed PROMs score would be presented.

Implant Survivorship

- Survivorship of the OR3O Dual Mobility System (assessed by revision for any reason) will be summarized using Kaplan-Meier survival tables and graphs. Time to revision will be the endpoint of interest, for subjects who die, are lost to follow-up or do not encounter the event of interest by the time of study termination would be censored on these dates.
- Survivorship of the controlled system up to 2 years after surgery (assessed by revision for any reason), Kaplan-Meier survival tables analogous to that specified for the OR3O Dual Mobility system will be implemented here as well.

Harris Hip Score (HHS)

- HHS scores for each subject will further be categorized as follows: Excellent (90-100); Good (80-89); Fair (70-79); Poor (60-69) and; Very poor (<60). Shift tables from the preoperative visit to all postoperative visits using these classifications will be generated.
- The total HHS and the scores for each of its following subdomains: pain, function, absence of deformity, and range of motion will be summarized using continuous summary characteristics by preoperatively and postoperatively at 6 weeks, 3 months, 6 months, 1 year and 2 years (i.e. by visit). For the HHS and its subdomain scores, independent repeated measurement Analysis of Covariance (ANCOVA) model (with visit as the repeated term) will be used to model the change from preoperative to postoperative with total HHS (and its

CONFIDENTIAL AND PROPRIETARY

This document contains information that is confidential and proprietary to Smith & Nephew PLC and Smith & Nephew, Inc. and is intended for use only by Smith+Nephew and its manufacturer. It shall not be reproduced or copied in whole or in part, nor shall the contents be disclosed by any means without prior written permission from Smith+Nephew, nor shall anyone make any use of it that is contrary to the expressed or implied wishes of Smith+Nephew.

Statistical Analysis Plan

A Prospective, Multi-center, Randomized, Controlled Study to Evaluate the
Safety and Efficacy of the OR3O™ Dual Mobility System versus conventional
single bearing design Total Hip System in Primary Total Hip Arthroplasty (THA)Version: 2.0,
29-Feb-2024

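### Kaplan-Meier implant survivorship censors unrevised hips on the loss-to-follow-up or study-termination date, which can fall months after implant status was last known

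*SAP*

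**What the plan says.** SAP 7.11 (Implant Survivorship) summarises time to revision with Kaplan-Meier tables and graphs for each arm. After naming deaths, it covers subjects who are "lost to follow-up or do not encounter the event of interest by the time of study termination would be censored on these dates". Protocol 10.4.2 has the same rule: subjects who "do not encounter the event of interest by the time of study termination would be censored on these dates". SAP 7.12 also uses Kaplan-Meier for shell, head and stem survivorship, with no censoring rule of its own.

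The time variable in SAP 7.4 is defined only for revised hips. The formula begins "Time to revision (in months) = (Revision Date" and subtracts the operative date. There is no matching formula for a censored hip, and SAP 7.3 has no rule for missing implant status.

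Four protocol provisions decide what those dates mean in practice:

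- Protocol 7.7 sets the test for declaring a loss: "he/she does not appear for the scheduled study visit for 2 consecutive visits, and study personnel are unable to contact the subject".
- Protocol 9.2.1: "Information on implant / component survivorship will be derived from adverse event in eCRFs".
- Protocol 9.1.4 to 9.1.6, at each follow-up visit: "Verify with subject if any revision has occurred since last visit". Also: "In case the follow-up visit was missed, contact the subject by telephone to collect information on implant status and adverse events".
- Protocol 20 defines the end of the study once, for the whole population.

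**The concern.** A Kaplan-Meier estimate is sound when every hip in the risk set is one whose revision would have been seen. Here a subject must be out of contact through two scheduled visits before being called lost. During that time no adverse event form can be completed, so a revision would go unrecorded. If the hip is then censored on the later date, that silent interval is counted as revision-free.

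Subjects who withdraw or are withdrawn (Protocol 7.8.2 and 7.8.3) do not appear in the censoring list. They have no revision by study termination, so they fall under that clause by default. The documents do not say whether the term means the end of the whole study or the subject's own exit.

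What is at stake is survivorship in both arms. It is among the analyses that SAP 2.0 keeps after dropping the primary test, the change-from-baseline models and the dislocation comparison.

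**Working it through.** The documents give no survivorship rate, event count or precision, so there is no stated figure to reproduce. Two things can be worked out: the gap that the rule creates, and an illustration of its effect.

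**1. Gap between last observation and declared loss.** Inputs are the visit windows in Protocol 9.1 and SAP Table 1 (42 −7/+14, 90 ±30, 180 ±30, 365 ±60 and 730 ±60 days), the two-missed-visit rule in Protocol 7.7, and the SAP's 30.4375 days per month. Gap = (day of second missed visit − day last seen) / 30.4375.

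| Last seen | Second missed visit | Nominal gap | Range from windows |
|---|---|---|---|
| 6 weeks (42) | 6 months (180) | 138/30.4375 = 4.5 months | 3.1 to 5.7 |
| 3 months (90) | 1 year (365) | 275/30.4375 = 9.0 months | 6.1 to 12.0 |
| 6 months (180) | 2 years (730) | 550/30.4375 = 18.1 months | 15.1 to 21.0 |

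A hip last seen at 1 year has only one scheduled visit left, so it cannot meet the two-visit rule. If carried to the 2-year point it adds 365/30.4375 = 12.0 nominal months (up to 15.9).

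**2. Direction.** Each Kaplan-Meier step is 1 − d/n. Compared with censoring at last known status, the stated rule leaves the observed revisions d unchanged and can only raise n. Each step therefore rises or stays the same.

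**3. Share of follow-up affected (illustration).** SAP 6.1 plans 85 hips per arm with 76 evaluable, so 85 − 76 = 9 lost. Assume all 9 were last seen at 6 months and stay at risk to 24 months. Unobserved time is 9 × 550 = 4,950 hip-days out of 85 × 730 = 62,050, or 8%.

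**4. Effect on the estimate (illustration).** Also assume a constant revision hazard. One quarter of the two-year risk then falls before month 6, and three quarters falls in the period when only 76 of the 85 hips counted at risk are observed. To first order:

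- True 5%: 1.25% + 3.75% × 76/85 = 1.25% + 3.35% = 4.6%.
- True 2%: 0.5% + 1.5% × 76/85 = 0.5% + 1.34% = 1.84%.

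**5. Cross-check with discrete events.** Put k observed revisions at month 18 and compare 1 − k/85 with 1 − k/76:

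- k = 1: 98.82% against 98.68%, a difference of 0.14 points.
- k = 2: 97.65% against 97.37%, a difference of 0.28 points.
- k = 4: 95.29% against 94.74%, a difference of 0.56 points (from unrounded values).

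The two illustrations agree in direction and scale.

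**The case against.** The strongest reply is that the dates are undefined rather than wrong. If the loss date were programmed as the last contact, and study termination as the subject's own exit, there would be little or no gap. The documents do use termination at subject level: Protocol 7.8.1 has subjects terminate the study after revision surgery, and SAP 7.6 speaks of hips terminated from the study and of termination visits. Status is also checked at exit. Protocol 9.1.6 applies the final visit on withdrawal too, with a telephone fallback, and Protocol 9.1.9 asks for a full exit visit where possible. Protocol 7.8.2 lists stopping of the study as a ground for withdrawal, so subjects stopped early may be seen or telephoned then.

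This narrows the point for withdrawn and stopped subjects. It does not remove it for lost subjects: by definition they were not reached, and the two-visit rule puts the label after the last observation.

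A reader might infer more than the documents support:

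- *That the bias is always in the implant's favour.* If no revision is observed while unobserved hips are wrongly at risk, the estimate does not move. Never unfavourable is the most that can be said.
- *That withdrawn subjects are certainly carried to the study-level end.* The text allows either reading.
- *That early termination makes the problem large.* Exit contacts could bring last status and termination close together, and the termination date, actual enrolment and losses are not given.
- *That the figures above are estimates for this trial.* They are near the worst case: full planned enrolment, all attrition at 6 months, none of it from death or from withdrawal with an exit visit.
- *That published confidence limits will be too narrow.* SAP 7.11 specifies none for survivorship and no test between arms.
- *That the blank implant-status cell at 3 months contributes.* It is a separate inconsistency in the schedule tables. Protocol 9.1.5 already requires the revision query at that visit, and the cell has no bearing on censoring.

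**Conclusion.** The point holds in a limited form. As written, the rule can keep hips in the risk set after their status is last known. For subjects lost under Protocol 7.7 the nominal excess is about 4.5 to 18 months, depending on the last visit attended. For withdrawn subjects the rule is silent and can be read two ways. Censoring at death is not in dispute.

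The rule overstates survivorship or leaves it unchanged. At the planned attrition the overstatement is about 0.2 points for a 2% two-year revision rate and 0.4 points for 5%. Those sizes rest on the assumed loss at 6 months, constant hazard and retention to 24 months. The real effect cannot be calculated from the documents. The endpoint is secondary and descriptive, so this is a correction to the plan and not a threat to its main conclusion.

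**What to change.** In SAP 7.11 and 7.12, and in Protocol 10.4.2, state that hips without revision are censored at the last date on which implant status was known: scheduled visit, telephone contact, unscheduled or exit visit, or death. Say explicitly that this covers subjects lost to follow-up, withdrawn or stopped by early termination. Define that date in SAP 7.4 beside the time-to-revision formula.

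The cost is SAP and protocol wording plus one derived date. No new data are needed: Protocol 9.1.4 to 9.1.6 already collect implant status at visits or by telephone, and 9.1.7 does so at unscheduled visits.

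There are two downsides. Reported survivorship may be slightly less favourable or less precise. There is also a small asymmetry: a revision reported between visits counts as an event, while event-free time after the last contact does not, which can pull survivorship slightly down for subjects still in touch with their site.

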7.12 Analysis of Exploratory Endpoints

Survivorship of compatible components up to 2 years

Survivorship of acetabular shell, femoral head, and any of the femoral stems will be estimated by cumulative proportion of hips without revision of the respective components due to any reason, up to 2 years. The cumulative implant survival rates will be summarized using KM product limit estimates. This will be summarized using the SAF analysis population.

Dislocation percentage of the hip up to 2 years after device implantation

The cumulative dislocation percentage at the interim visits up to 2 years after device implantation, $p_{dis,i}$ will be compared to a literature specified percentage, $p_{literature}$. These literature-specified

CONFIDENTIAL AND PROPRIETARY

This document contains information that is confidential and proprietary to Smith & Nephew PLC and Smith & Nephew, Inc. and is intended for use only by Smith+Nephew and its manufacturer. It shall not be reproduced or copied in whole or in part, nor shall the contents be disclosed by any means without prior written permission from Smith+Nephew, nor shall anyone make any use of it that is contrary to the expressed or implied wishes of Smith+Nephew.

Statistical Analysis Plan

A Prospective, Multi-center, Randomized, Controlled Study to Evaluate the
Safety and Efficacy of the OR3O[™] Dual Mobility System versus conventional
single bearing design Total Hip System in Primary Total Hip Arthroplasty (THA)Version: 2.0,
29-Feb-2024
Page: 25 of 27ProceduresProcedures

Number: OR3O.2019.10 ST: 1100 Version: 2.0, 29-Feb-2024 Page: 25 of 27

percentages will be specified prior to database lock for final analyses. For the estimation of dislocation rate, a hip with multiple dislocations on-study will be counted only once. Two-sided exact 95% CIs will be estimated for p_{dis,i} where i is the visit at which the cumulative dislocation will be estimated (i.e. at 3months, 6 months, 1 year and 2 years). This will be summarized using the SAF population. One of the following conclusions will be made:

- If the lower limit (LL) of the two-sided 95% CI for $p_{dis,i}$ is > $p_{literature}$, then it is concluded that the dislocation rate on-study is significantly greater than the literature-specified rate.
- If the upper limit (UL) of the two-sided 95% CI for $p_{dis,i} < p_{literature}$, then it is concluded that the dislocation rate on-study is significantly less than than the literature-specified rate.
- If (LL of 95% CI of $p_{dis,i} \le$ pliterature \le UL of 95% CI of $p_{dis,i}$), then the dislocation rate on-study is comparable to that specified in literature.

However, as this study has been early terminated the study no longer has sufficient power for this test to be relevant and it will therefore not be performed. Descriptive summary statistics will be present for $p_{dis,i}$.

Hospital readmission percentage (cumulative) within 30, 60 and 90 days of discharge

The readmission percentage by 30, 60 and 90 days of discharge, p30,60,90 will be descriptively summarized as counts (n) and percentages (%). This will be summarized using the SAF analysis population.

7.13 Analysis of Safety Endpoints

The following summaries will be performed on the safety endpoints:

• The number of adverse events will be reported both overall and by seriousness, relationship to study device and/or study procedure and expectedness.

CONFIDENTIAL AND PROPRIETARY

This document contains information that is confidential and proprietary to Smith & Nephew PLC and Smith & Nephew, Inc. and is intended for use only by Smith+Nephew and its manufacturer. It shall not be reproduced or copied in whole or in part, nor shall the contents be disclosed by any means without prior written permission from Smith+Nephew, nor shall anyone make any use of it that is contrary to the expressed or implied wishes of Smith+Nephew.

Statistical Analysis Plan

A Prospective, Multi-center, Randomized, Controlled Study to Evaluate theVersion: 2.0,Safety and Efficacy of the OR3O[™] Dual Mobility System versus conventional29-Feb-2024single bearing design Total Hip System in Primary Total Hip Arthroplasty (THA)Page: 26 of 27ProceduresProcedures

Number: OR3O.2019.10 ST: 1100 Version: 2.0, 29-Feb-2024 Page: 26 of 27

- The number of subjects experiencing adverse events will be summarised both overall and by seriousness, relationship to study device and/or study procedure and expectedness.
- An overall AE summary table that will summarize as number (n) and percentages (%), the overall incidence according to subjects with at least one AE; subjects with at least one AE by worst severity (mild, moderate, or severe); subjects with at least one AE by worst outcome (resolved, ongoing/unresolved, or death); subjects with an AE that led to study discontinuation and; subjects with at least one AE by worse relatedness to device. Other events such as SAEs, ADEs, SADEs or ASADEs, USADEs will also be similarly summarized using number (n) and percentages (%).
- Incidence of device- or procedure-related re-interventions that occur on-study will be summarized as number (n) and percentages as well as by type.
- Device deficiencies that occur on-study will be listed.

All safety endpoints will be summarized using the SAF analysis population.

